7.1.1 First Dose of the Study Drug

The dose of the study drug taken on the day prior to surgery will count as the first dose of the study drug.

It is possible that a subject is scheduled to have their surgery on a certain date, and according to the protocol, they take a drop of the study drug one day prior, however, then the surgery is rescheduled to a later date. In this case the subject would keep the IP, stop taking it, and apply a new drop before the new scheduled date of surgery. The very first drop taken prior to the date of cancelled surgery will count as the first dose of the study drug only for the purposes of determining the treatment-emergent status of AEs. It will not count as the first dose of the study drug for any other purposes, including, but not limited, to the following:

1. definition of baseline;
2. reference date for calculation of relative days;
3. calculation of study drug exposure and compliance.

Instead, the dose taken prior to the actual surgery will be considered as the first dose of the study drug.

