#### 5.3 Corneal Effects

Use of topical NSAIDs may result in keratitis. In some susceptible patients, continued use of topical NSAIDs may result in epithelial breakdown, corneal thinning, corneal erosion, corneal ulceration or corneal perforation. These events may be sight threatening. Patients with evidence of corneal epithelial breakdown should immediately discontinue use of topical NSAIDs including ILEVROTM (nepafenac ophthalmic suspension), 0.3% and should be closely monitored for corneal health.

Postmarketing experience with topical NSAIDs suggests that patients with complicated ocular surgeries, corneal denervation, corneal epithelial defects, diabetes mellitus, ocular surface diseases (e.g., dry eye syndrome), rheumatoid arthritis, or repeat ocular surgeries within a short period of time may be at increased risk for corneal adverse events which may become sight threatening. Topical NSAIDs should be used with caution in these patients.

Postmarketing experience with topical NSAIDs also suggests that use more than 1 day prior to surgery or use beyond 14 days post-surgery may increase patient risk and severity of corneal adverse events.

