All information pertaining to adverse events noted during the study will be listed by subject, detailing verbatim, preferred term, system organ class, start date, stop date, intensity, outcome, action taken, and causal relationship to the study drug. The adverse event onset will also be shown relative (in number of days) to the date of first administration of the study drug. In addition, the adverse event duration (if AE Stop Date is available) will be evaluated as below and presented (in number of days).

$$\text{AE Duration} = \text{AE Stop Date} - \text{AE Start Date} + 1$$

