7.8.9 Exposure to Product

The subjects will be instructed to use the diary to document all doses taken. Additionally, the dose taken one day prior to the surgery will be recorded on the eCRF.

Compliance with scheduled application of IP will be determined from the subject's diary as $[\text{Actual number of doses}] / [\text{Planned number of doses}] * 100\%$, where

- Actual number of doses will counted from the subject diary and relevant eCRF pages;
- Planned number of doses is 17 (i.e. Days -1 through Day 14 with two doses taken on Day 0).

Number of missed doses will be calculated as the number of planned dosing time-points when the study drug was not taken during the 16 days starting with the date of the first dose. There is one dosing time-point per each day, except the day of Visit 2 Day 0, when there are two planned time-points, before the surgery and after the surgery.

Subjects who missed dosing for more than 3 consecutive days will be considered non-compliant and will be excluded from the PP population.

Subjects can be additionally excluded from the PP population due to non-compliance, if the Investigator's and Sponsor's review of their dosing times suggests a clinically meaningful departure from the once-daily dosing pattern.

Subjects will be considered compliant if they administer at least 14 doses and not more than 20 doses, with no more than 3 consecutive missed dosing days. The compliance will be analyzed using the descriptive statistics by treatment group. The proportion of compliant vs. non-compliant subjects will be tabulated for each treatment.

Duration of exposure will be calculated as Date of last use of the study drug – Date of first use of the study drug + 1. Duration of exposure will be summarized descriptively by treatment group.

Compliance, number of doses and duration of exposure will be summarized for the Safety and mITT populations.

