7.8.10 Exposure to Concomitant Medication

Medication or non-drug therapy will be classified as prior, if the end date is known and is prior to the first use of the study drug. Medications and non-drug therapies that are ongoing or ended after the first use of the study drug will be classified as concomitant. If the end date of the medication or non-drug therapy is unknown, it will also be considered concomitant.

The concomitant medications will be summarized by preferred term for each treatment group as coded by the World Health Organization Drug (WHODRUG) dictionary Sept-2017 and be listed in a by-subject listing. Prior medications will be listed only.

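### SAP 7.1.1 ignores a drop taken before a cancelled surgery for AE onset day, prior/concomitant status and exposure, so real earlier use is misdated or not summarised

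*SAP*

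**What the plan says.** SAP 7.1.1 foresees that a subject may take the Day -1 drop, have surgery postponed, stop, and start again before the new date. The early drop is the first dose "only for the purposes of determining the treatment-emergent status of AEs". For the rest the SAP states: "It will not count as the first dose of the study drug for any other purposes, including, but not limited, to the following". The three named items are the definition of baseline, the "reference date for calculation of relative days", and the "calculation of study drug exposure and compliance". The drop before the surgery that takes place becomes the first dose instead.

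Three later sections depend on a first-dose date:

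- **SAP 7.8.1, AE listings:** "The adverse event onset will also be shown relative (in number of days) to the date of first administration of the study drug".
- **SAP 7.8.9, exposure:** "Duration of exposure will be calculated as Date of last use of the study drug – Date of first use of the study drug + 1". The planned course is 17 doses. Actual doses come from the diary and eCRF, and this section does not say whether the early drop is left out.
- **SAP 7.8.10, other treatments:** a medicine or other therapy is prior when its end date is available and falls before study drug was first used. Prior medications are listed only; concomitant ones are also summarised.

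The label in protocol Appendix III (label section 5.3) gives this caution on timing: "use more than 1 day prior to surgery or use beyond 14 days post-surgery may increase patient risk and severity of corneal adverse events". Protocol 12.6 plans a descriptive exposure summary and names no dose to be excluded. Protocol 9.0 and 11.7 apply limits of 14 and 20 doses to all study drug taken over the trial. SAP section 8 declares no change from the protocol's analyses.

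**The concern.** A subject whose surgery is postponed after the Day -1 drop has had study drug more than one day before the actual surgery. Under 7.1.1 the SAP treats that drop as drug when it decides whether an event is treatment-emergent, and as not yet drug when it dates the event, classifies medicines and summarises exposure. One subject then has two starting points, and only one of them appears in the output.

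What is at stake is how safety data read at subject level. An event that followed study drug can be shown with an onset before the first administration. A medicine given for that event can be labelled as used before treatment. The exposure tables show an ordinary course for a subject whose timing is of the kind the label cautions about. No efficacy result is involved.

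**Working it through.** **Inputs.** Planned course and exposure formula: SAP 7.8.9. Relative-day formulas: SAP 7.1. First-dose rule: SAP 7.1.1. The delay k, in days, is not in the documents. I take 1 to 20, so that the early drop falls no earlier than Day -21, the outer limit of the protocol's screening window. The seven-day window printed in SAP 11.1 would cap k at 6.

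**Step 1: the plan's own figure.** Day -1 to Day 14 is 14 - (-1) + 1 = 16 days. One extra dose on Day 0 gives 17 doses. This matches SAP 7.8.9.

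**Step 2: dates.** The restarted course begins on Day -1 of the actual surgery. The early drop falls on Day -(k + 1), which is more than one day before surgery for every k of 1 or more. The days without drug between the two number k - 1.

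**Step 3: AE onset day.** For an event before the first dose, relative day = event date - first-dose date. For an event on the day of the early drop this is -(k + 1) - (-1) = -k. Measured from the very first drop it is day 1.

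| k | Early drop | Undosed days, k - 1 | Onset day, SAP | Onset day, very first drop | First-to-last span, 16 + k |
|---|---|---|---|---|---|
| 1 | Day -2 | 0 | -1 | 1 | 17 |
| 4 | Day -5 | 3 | -4 | 1 | 20 |
| 5 | Day -6 | 4 | -5 | 1 | 21 |
| 7 | Day -8 | 6 | -7 | 1 | 23 |
| 20 | Day -21 | 19 | -20 | 1 | 36 |

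**Step 4: medicines.** Take k = 7. A medicine given from Day -5 to Day -3 ends before Day -1, so it is prior under 7.1.1 and leaves the summary. Judged against the very first drop on Day -8 it is concomitant. 7.1.1 does not name medication classification, but its wording covers any purpose other than treatment-emergent status.

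**Step 5: duration.** The SAP reports 16 days whatever k is. Putting the early drop into last minus first plus 1 gives 16 + k, but k - 1 of those days had no drug. At k = 10 the span is 26 days: 17 dosing days and 9 undosed days. The SAP figure omits 1 dosing day; the wider span adds 9 days without drug.

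**Step 6: dose count.** With the early drop, a fully dosed subject took 17 + 1 = 18 doses, and 18/17 = 105.9% against 100.0%. If a pre-operative drop was also given on the cancelled day, the total is 19. One added dose changes status against the 14-to-20 limits only at the edges: 13 becomes 14, or 20 becomes 21.

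**Step 7: group level.** If a share m of subjects had one early drop, mean doses are 17 + m: 17.01, 17.05, 17.10 and 17.20 for m = 1%, 5%, 10% and 20%. All these shares are assumptions. For scale, 2% to 5% of about 450 subjects is 9 to 22.5.

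**The case against.** The convention has a sound reason. If the early drop started the course, the gap would read as missed dosing. It reaches 3 consecutive days at k = 4 and exceeds 3 at k = 5, which are the triggers in protocol 9.0 and SAP 7.8.9 respectively. A negative onset day also follows from a declared rule. Both points stand, and they are why the rule should stay for baseline and for compliance with the planned course. Neither requires AE onset or medication status to use the later date.

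Several stronger readings are tempting, and the documents do not support them:

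- **That AEs are lost or AE rates are too low.** Treatment-emergent status runs from the early drop, entry to the safety population needs evidence of only one dose, and AE percentages are subjects over subjects, not events over exposure time.
- **That a corneal event could not be traced to the early drop.** By-subject listings carry AE dates, surgery details, drug and diary accountability, and both prior and concomitant medicines. What is missing is a summary by arm.
- **That 17 doses will certainly be reported where 18 were taken.** 7.1.1 removes the drop from exposure and compliance, while 7.8.9 counts from the diary and eCRF with no stated exclusion. Two programmers could reach 17 or 18.
- **That the upper dose limit is undermined.** Totals of 18 or 19 are within 20 on either count.
- **That duration is understated by the whole delay.** Step 5 shows that most of the added span is undosed.
- **That the label describes this exact case.** It speaks of use more than one day before surgery and does not discuss a single drop followed by a stop and a restart.

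**Conclusion.** The point holds as a defect in safety reporting for subjects whose surgery was postponed after dosing. For each of them, events in the gap can be treatment-emergent with onset days from -k to -1; medicines that ended in the gap are prior and unsummarised; and no exposure summary shows use k + 1 days before surgery. The treatment of the early drop in the dose count is unsettled between SAP 7.1.1, SAP 7.8.9 and protocol 9.0 and 11.7.

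The size is small at group level and depends on an unknown number of postponed surgeries. The primary equivalence and superiority analyses, the TEAE tables and the AE percentages do not change. The onset-day and duration figures rest on one early drop, a complete restarted course, and the assumed range of k.

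**What to change.** 1. Keep 7.1.1 for baseline and for compliance with the 17-dose course, and leave duration of exposure on the restarted course, because the gap is undosed.
2. Add one derived variable, the date of the very first drop. Use it for AE onset day in 7.8.1 and for prior/concomitant classification in 7.8.10.
3. Report by arm the number of subjects with a drop before a cancelled surgery, the days from that drop to the actual surgery, and total drops taken including it.
4. Reconcile SAP 7.1.1 and 7.8.9 with protocol 9.0 and 11.7 on whether the early drop enters the dose count. Which count applies is for the sponsor to settle; the documents must give the same answer.

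The cost is SAP wording, one variable and one short table. The treatment-emergent rule in 7.1.1 already needs the date of the early drop, so no new data should be required. The downside is two first-dose dates for a few subjects, which a footnote in the affected outputs can explain.

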7.2 Subject Disposition

The number of subjects screened in the study, randomized to treatment, included in the Safety, PP, mITT populations, prematurely discontinued from the study (along with the reasons for discontinuation) will be calculated. The percentages will be based on the number of subjects randomized to each treatment group. Percentages for discontinuation reasons will be based on the sub-population of subjects who discontinued from the study.

Number and percentage of subjects enrolled by site will be tabulated for all enrolled subjects, Safety, mITT, and PP populations.

7.3 Demographic and Baseline Characteristics

Demographic characteristics will include:

- age;
- gender;
- race;
- ethnicity;

Baseline characteristics include:

- height, weight, body mass index (BMI)
- iris color
- aqueous cells grade for the study eye
- aqueous flare grade for the study eye
- ocular pain grade for the study eye

Descriptive statistics will be presented for age (years), height, weight and BMI. Frequency counts and percentages will be presented for race, ethnicity, iris color and baseline grades.

Height will be reported in centimeters and weight in kilograms.

Age will be derived from Informed Consent Signed Date (INFCSD) and Date of Birth (DOB) as the number of whole years between those two dates.

Demographic and baseline characteristics will be evaluated for comparability across treatment groups in the following manner. Continuous variables (age, height, weight, BMI) will be analyzed with an ANOVA with factors of treatment and investigational site. Overall p-value for the global null hypothesis of all groups being equal will be displayed. Categorical variables (gender, ethnicity, race, iris color, baseline grades) will be analyzed with a Cochran-Mantel-Haenszel general association test, stratified by investigational site.

These analyses will be performed for Safety, mITT, and PP populations.

All parameters reported during screening or baseline phase (including informed consent information, inclusion/exclusion criteria, randomization information, method of contraception, etc.) will be presented in by-subject listings.

7.4 Medical History

Medical history will be summarized by MedDRA (version 20.1) System Organ Class (SOC) and Preferred Term for the safety population. Each subject will be counted once within each applicable SOC and Preferred Term. All medical history information collected on the eCRF will also be listed.

7.5 Protocol Deviations

Protocol deviations will be derived algorithmically (programmable) as well as reported by sites (observable). Each protocol deviation will be classified as minor or major. In the case there are differences in the programmable vs. observable protocol deviations, the programmable protocol deviation will take precedence. Specific deviation and their severity are defined in the separate Protocol Deviations List document.

All major protocol deviations will be summarized by deviation category and treatment group. This analysis will be performed for the Randomized set.

7.6 Cataract Surgery

All details of the surgery captured on the eCRF will be listed.

7.7 Efficacy Analyses

7.7.1 Analyses of Primary Endpoint

The primary efficacy endpoint is the proportion of subjects with cure at Visit 5 (end of the study on Day 14+/-2). A subject is defined as cure if they have a score of 0 for aqueous cells, a score of 0 for aqueous flare and a score of no more than 3 for pain in the study eye. A subject is defined as failure if they have a score of >0 for aqueous cells, or score of >0 for aqueous flare or a score of >3 for pain in the study eye.

[REDACTED]

The denominator for percentages will be the number of subjects with either cure or failure, i.e. subjects without a valid assessment will be excluded.

7.7.1.1 Analysis of clinical equivalence of test and reference treatments

A two-sided, continuity-corrected, 90% confidence interval on the Test-to-Reference difference for the proportion of subjects with cure will be constructed. Bioequivalence will be established if the 90% confidence interval for the difference is contained within the interval [-0.20, +0.20] for the PP population.

Analysis of bioequivalence will be performed on the PP population.

7.7.1.2 Analysis of superiority to placebo

The evaluation of superiority will be conducted separately for the Test treatment versus the Placebo treatment and for the Reference treatment versus the Placebo treatment, comparing the proportions of subjects with cure. The analysis will be conducted using two-sided Fisher's exact test.

Superiority will be established if the cure proportion for each active treatment is greater than, and statistically significantly different from ($p < 0.05$ for the Fisher's test) that of the Placebo for the mITT population. Analysis of superiority will be performed on the mITT population.

7.7.2 Analyses of Individual Efficacy Parameters

Aqueous cells, aqueous flare and ocular pain will be assessed at Visits 1, 3, 4 and 5. Aqueous cells will be assigned a grade from 0 (None) to 4 (Greater than 30 cells) (see section 11.2 for complete scale); aqueous flare a grade from 0 (No visible flare when compared with the normal eye) to 3 (Very dense flare) (see section 11.3 for complete scale). Ocular pain will be graded from 0 (None) to 5 (Severe) (see section 11.4 for complete scale).

Number and percentage of subject at each grade for aqueous cells, aqueous flare and ocular pain in the study eye will be tabulated by visit. This analysis will be performed for both mITT and PP populations.

7.8 Safety Analyses

7.8.1 Adverse Events

Adverse Events will be coded using the MedDRA, Version 20.1, AE coding system for purposes of summarization.

Only Treatment Emergent Events (TEAEs) will be used for the summary analysis. An AE will be considered as treatment-emergent if the time of onset is after the time of the first study drug administration or if it increased in severity during the study period. AEs with unknown start dates will be counted as treatment-emergent unless the AE resolution date is prior to the study drug start date. If the start date is partially missing, then month and year (when available) will be used to determine if the event occurred prior to or post dosing.

A TEAE is considered as treatment-related if it is recorded as Related on the eCRF. In case the relatedness was not assessed, the most conservative result – related – will be chosen for the analysis.

An overall summary will include, by treatment group and overall, the number of TEAEs and the number and percentage of subjects reporting at least 1 TEAE, as well as number of TEAEs in the following categories:

- Any TEAE,
- Treatment-related TEAE,
- Serious TEAE,
- TEAE leading to discontinuation of the study medication.

The following TEAE frequency tables will be prepared summarizing the number and percentage of subjects reporting at least one TEAE by MedDRA SOC and PT:

- All TEAEs,
- TEAEs by Severity,
- TEAEs by Relationship to Study Medication.

These AE summaries will be presented in alphabetical order of SOC and preferred terms.

Additionally, TEAEs will be summarized by the preferred terms in the descending order of frequency in the total treatment group. In this table a p-value from Fisher's exact test

comparing event rates between the Test and the Reference treatment groups will be provided for those preferred terms that have frequency > 1% in either Test or Reference group.

A subject experiencing the same AE multiple times will only be counted once for that preferred term. Similarly, if a subject experiences multiple AEs within the same system organ class, that subject will be counted only once in that system organ class. In summaries by severity and relationship each subject will be counted with the highest applicable severity and the closest applicable relationship.

All information pertaining to adverse events noted during the study will be listed by subject, detailing verbatim, preferred term, system organ class, start date, stop date, intensity, outcome, action taken, and causal relationship to the study drug. The adverse event onset will also be shown relative (in number of days) to the date of first administration of the study drug. In addition, the adverse event duration (if AE Stop Date is available) will be evaluated as below and presented (in number of days).

$$\text{AE Duration} = \text{AE Stop Date} - \text{AE Start Date} + 1$$

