Worsening of the disease under study will be measured by evaluation of pain and inflammation. The evaluation of pain and inflammation should be recorded as an adverse event only if the presentation and/or outcome is more severe than would normally be expected from the normal course of the disease in a particular patient.

A treatment-emergent AE is any AE that occurs after initiation of study medication, or any event already present that worsens in either intensity or frequency following exposure to study medication.

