## **13.5 Recording and Reporting of Adverse Events**

In this study, safety will be assessed by qualified study personnel by evaluating reported adverse events, clinical laboratory test results, vital signs measurements, physical examination findings (including body weight and height measurements), and use of concomitant medication.

For adverse event recording, the study period is defined for each subject as that time period from signature of the informed consent form through the end of the study (including the follow up period).

All adverse events that occur during the defined study period must be recorded on the source documentation, regardless of the severity of the event or judged relationship to the study drug. For serious adverse events, the Serious Adverse Event Form must also be completed, and the serious adverse event must be reported immediately (see Section 13.8). The investigator does not need to actively monitor subjects for adverse events once the study has ended. However, serious adverse events occurring in a subject after the treatment of that subject has ended should be reported to the sponsor if the investigator becomes aware of them.

At each contact with the subject, the investigator or designee must question the subject about adverse events by asking an open-ended question such as, "Have you had any unusual symptoms or medical problems since the last visit? If yes, please describe." All reported or observed signs and symptoms will be recorded individually, except when considered manifestations of a medical condition or disease state. A precise diagnosis will be recorded whenever possible. When such a diagnosis is made, all related signs, symptoms, and any test findings may be recorded collectively as a single diagnosis on the CRF and, if it is a serious adverse event, on the Serious Adverse Event Form.

The onset and end dates and times, action taken regarding study drug, treatment administered, and outcome for each adverse event must be recorded on the source documentation.

The relationship of each adverse event to study drug treatment and study procedures, and the severity and seriousness of each adverse event, as judged by the investigator, must be recorded as described above.

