8. CHANGES FROM PROTOCOL-SPECIFIED ANALYSES

There are no changes from the protocol-specified analyses.

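### The SAP's treatment-emergent rule for worsening adverse events is not tied to the first dose and omits frequency, an undeclared departure from the protocol's definition

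*SAP*

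**What the plan says.** Protocol 13.1 defines a treatment-emergent adverse event (TEAE) in two limbs. The first covers events that begin once study medication has started. The second covers "any event already present that worsens in either intensity or frequency following exposure to study medication".

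SAP 7.8.1 keeps the first limb. Its second limb reads "or if it increased in severity during the study period". The SAP does not say what the study period is. The only definition in either document is in Protocol 13.5: "the study period is defined for each subject as that time period from signature of the informed consent form", running to the end of the study with follow-up included. The opening words of that sentence limit it to the recording of adverse events.

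The rule governs what is tabulated, because SAP 7.8.1 says that only TEAEs "will be used for the summary analysis". The same section gives a Fisher p-value for Test against Reference "for those preferred terms that have frequency > 1% in either Test or Reference group".

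SAP 7.1.1 deals with postponed surgery. A drop taken before a cancelled operation counts as the first dose "only for the purposes of determining the treatment-emergent status of AEs". SAP 8 states: "There are no changes from the protocol-specified analyses".

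**The concern.** TEAE incidence is a named safety endpoint in both documents, and they define it differently. Protocol 12.0 makes the SAP the working record of the statistical evaluation, so a programmer will code the SAP wording.

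Two things are lost between protocol and SAP. One is the requirement that worsening follow exposure; the other is frequency as a form of worsening. The first loss can bring in events that no product could have caused. The second can leave out events that the protocol wants counted. A reader of the safety tables would not learn of either, because the SAP reports no departure.

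**Working it through.** No sample size, power or alpha figure is involved, so the check sets the two definitions side by side.

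**Inputs**
- Adverse events are recorded from consent (Protocol 13.1 and 13.5).
- Consent is taken at Visit 1, and screening may last up to 21 days (Protocol Synopsis and 8.1).
- The first dose is taken the day before surgery (SAP 7.1.1). A pre-dose interval with recorded events can therefore exist.
- The SAP phrase can be read in two ways: as running from consent, or as the treatment period only.

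**Classification of each kind of event**

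| Event | Protocol 13.1 | SAP 7.8.1, from consent | SAP 7.8.1, treatment period only |
|---|---|---|---|
| A. Starts after first dose | TEAE | TEAE | TEAE |
| B. Starts before first dose; severity rises only before first dose | Not TEAE | TEAE | Not TEAE |
| C. Starts before first dose; severity rises after it | TEAE | TEAE | TEAE |
| D. Starts before first dose; only frequency rises after it | TEAE | Not TEAE | Not TEAE |

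**Reasoning**
1. A and C agree on every reading.
2. B differs only if the study period starts at consent. This part of the point is conditional.
3. D differs on both readings, because the SAP limb mentions severity alone.
4. D is narrower than it looks. Protocol 13.1 already makes a significant change in the frequency of a preexisting condition an adverse event. Recorded with a post-dose onset, it enters through the SAP's first limb. What remains is an event that first arises between consent and first dose, persists, becomes only more frequent after dosing, and is not entered again by the site.
5. Both classes feed the TEAE counts. Through those counts they can change which preferred terms pass the 1% line and the p-values given for them. Protocol 12.6 plans no inferential analysis of adverse events, and no decision rule in the SAP uses these p-values.
6. The cure endpoint is built from cells, flare and pain scores, so the TEAE flag does not enter the equivalence or superiority tests.

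**The case against.** The best reply is that the authors meant the treatment period. The Protocol 13.5 definition is limited to adverse event recording, and the SAP does not cite it. The Protocol Synopsis equates the total study duration with the 16 days of treatment and mentions screening separately. SAP 7.1.1 fixes a first dose for treatment-emergent status, and the partial-date rule in SAP 7.8.1 asks whether an event came before or after dosing. All this makes a dose-anchored intent likely, which is why class B is stated conditionally. It does not supply the missing words. The phrase classifies adverse event data, and the only definition written for such data starts at consent. Nor does it restore frequency.

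Class B also needs an event that both starts and worsens before the first dose. No clinic visit is scheduled between Visit 1 and surgery, only the call on Day -1, and the planned listing shows one intensity per event. Whether a pre-dose rise in severity could be seen at all depends on the eCRF, which is not in the documents. This stands, and it limits the likely number of events.

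A reader might infer two stronger points that the documents do not support:
- *Mild dry eye present at entry would be lost when it flares more often.* Mostly not. It is a preexisting condition, so the Protocol 13.1 provision on frequency applies.
- *Pre-dose events would be tabulated as drug-related.* SAP 7.8.1 does have a default ("In case the relatedness was not assessed, the most conservative result", namely related). But Protocol 13.5 requires the investigator to record the relationship for each event, so this route supposes a lapse at the site that nothing in the documents predicts.

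**Conclusion.** The point holds as a definitional conflict. SAP 7.8.1 omits frequency and does not tie worsening to the first dose, and SAP 8 declares neither change. The frequency gap exists on any reading. The inclusion of pre-dose worsening depends on reading the study period as starting at consent.

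The effect is probably small and balanced across arms. For class B, balance follows from randomisation and masking, since no product has yet been given. For class D it is an assumption, resting on how narrow the class is and on one rule being applied to all arms.

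A reader might try to size the problem from the length of the pre-dose interval: up to 20 days (Day -21 to Day -2), or 6 days under the Day -7 window in SAP 11.1, and possibly none. Another route would be the number of subjects needed to pass the 1% line. Neither measures it. The interval is not a count of events, the 1% line applies under any TEAE rule, and the arm sizes are redacted. The documents give no number of affected events, so none is claimed. Nothing here bears on the efficacy or equivalence conclusions.

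**What to change.** In SAP 7.8.1, replace the second limb with: *or if an event already present before the first dose worsened in intensity or frequency after the first dose*. State that the first dose is the one SAP 7.1.1 sets for treatment-emergent status. Events that start, or start and worsen, only before that dose then stay in the by-subject listings that SAP 7.8.1 already plans, which show onset relative to first dose.

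Before programming, check how the eCRF would show post-dose worsening, because a frequency limb can be coded only if sites record the change. If the sponsor prefers its own wording, it should define the study period and declare the departure in SAP 8.

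The cost is one sentence in the SAP. No protocol amendment, visit or assessment is needed.
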